7.6 Blinding System and Emergency Unblinding Procedure

Medication bottles will be coded with unique randomization numbers. The dataset linking the randomization number to the actual treatment (clopidogrel or placebo) will be generated and maintained at the NETT-SDMC. The electronic file that contains partially unblinded treatment assignment (e.g., A=clopidogrel, B=placebo) will only be accessible to unblinded personnel when preparing unblinded (closed) reports for the DSMB.

Unblinding is likely to be rare in the study. There are no data suggesting that taking clopidogrel is a contraindication to thrombolytic therapy. A major hemorrhagic event may result in the discontinuation of study medications, but knowledge of treatment assignment is unlikely to change therapy for these subjects [154], and therefore, unblinding is likely to be unnecessary. However, in case of an emergency need for unblinding of a particular subject, the clinical site PI or his/her designee can call the POINT emergency call number ([name] or [contact]), activate the pager system, and enter a call-back number. Within 20 minutes, the UCSF CCC On-call Physician will return the call. If it is determined that unblinding is necessary, the UCSF CCC On-call Physician will log onto the WebDCU™ study database and initiate the unblinding request with the subject's ID number or randomization number. Once this is completed, the site PI or designee can log onto WebDCU and review the Randomization Form for the subject, which will have the treatment assignment displayed. The treatment assignment is revealed for 30 minutes only. After 30 minutes, the treatment assignment is concealed.

After the unblinding, the Randomization CRF will have a message stating that the subject's treatment assignment has been unblinded due to site request.

Prior to the unblinding, the randomization form will have a message that states: "Subject has NOT been unblinded". This process will generate an automatic email notification of the unblinding to the POINT Executive Committee.

8 SAFETY

8.1 Protection/Minimization of Risk

The greatest risk to subject health is the study medication, clopidogrel, when combined with aspirin. These agents have not been tested specifically after TIA and minor ischemic stroke, so rates of hemorrhage must be estimated from studies of stroke and acute coronary syndromes. All subjects in the study will receive aspirin. The benefits of aspirin outweigh its small excess risk of systemic and intracranial hemorrhage [64, 65].

Clopidogrel in combination with aspirin is likely to be associated with a small excess risk of major systemic hemorrhage (estimated at 1% for the study period) but no increased risk of life-threatening or intracranial hemorrhage [81, 116, 180]. The absolute increase in risk of life-threatening hemorrhage in the MATCH trial, which is most similar to POINT, was 1.3% (2.6% for the combination vs. 1.3% for clopidogrel alone), and this risk was spread out over 18 months follow-up. Subjects are followed for 90 days and only TIAs and minor ischemic strokes are included, so a 1% excess absolute risk is realistic, and is consistent with other trials. The combination may increase the risk of complications with interventions, such as endarterectomy, or may delay the performance of these procedures due to

concerns about bleeding risk. Clopidogrel is also associated with a very small risk of thrombotic thrombocytopenic purpura [181], probably less than 1 per 100,000.

Loss of privacy due to additional contact from investigators not involved directly in the subject's care is another potential risk. There is also a small risk of loss of confidentiality.

8.2 Serious Adverse Events

The greatest risk to subject health is hemorrhage due to the study drugs. To reduce this risk, subjects will be monitored carefully during the study. Medications will be stopped if bleeding or other major complications occur and before any elective procedure. To mitigate potential risk of dipyridamole, use of this drug will be prohibited.

Unexpected SAEs will be reported to the DSMB in a timely fashion and on a schedule that is determined by the DSMB.

8.2.1 Management of SAEs/Clinical Outcomes

WebDCU™ has an integrated web-based SAE/Clinical Outcome Reporting module that provides the mechanism by which serious adverse events or clinical outcomes are reported and reviewed. SAEs/clinical outcomes will then be made available to the appropriate Project Management staff and the designated blinded Clinician Event Coordinator (CEC) for review. Reviews are performed on-line. If additional documentation is required, this will be requested of the site by its overseeing organization (NETT or CRC) or the CEC. Integration of the Clinician Event Coordinator functionality into the data entry system facilitates rapid review and reporting of events to the DSMB and regulatory bodies. The CRC Medical Monitor is notified when an event is determined to be a serious, unexpected, adverse reaction by the CEC. The CRC Medical Monitor completes the Council for International Organizations of Medical Sciences (CIOMS) form and sends it to the country-level Regulatory Manager for sites outside the US. The country level manager submits the form to the country level regulatory agency.

8.3 Definitions

Adverse Event

An adverse event (AE) is any unfavorable and unintended sign (including a clinically significant abnormal laboratory finding), symptom, or disease temporally associated with the use of an experimental treatment regardless of whether it is considered related to the treatment (attribution of unrelated, unlikely, possible, probable, or definite). Each AE is a unique representation of a specific event used for medical documentation and scientific analysis.

Non-serious AEs are not being collected in the POINT trial, unless they qualify as a Clinical Outcome as defined in section 4.6.1.

Serious Adverse Event

A serious adverse event (SAE) is any adverse event that is fatal or life threatening, is permanently or substantially disabling, requires or prolongs hospitalization, results in a congenital anomaly or requires intervention to prevent permanent impairment or damage.

Unexpected (Unanticipated) Adverse Event

An unexpected AE is defined as an event that was “not anticipated” as a risk in the IRB or EC-approved protocol, consent form, or package insert, or an event that occurs at a greater frequency or intensity than anticipated.

Anticipated Adverse Event

Anticipated adverse events in this trial will be those previously described in the package insert for clopidogrel and those anticipated based on the natural history of TIA and minor ischemic stroke.

8.4 Classification of Adverse Events

Severity is used to describe the intensity of a specific event. Severity of SAEs/clinical outcomes will be documented using the NCI Common Terminology Criteria for Adverse Events Version 4.03 (CTCAE) (see Manual of Procedures). The CTCAE provides descriptive terminology that will be used for recording and reporting SAEs/ clinical outcomes that occur in POINT. The CTCAE provides a grading (severity) scale for each AE term and AEs are listed alphabetically within categories based on anatomy or pathophysiology. The CTCAE (v 4.03) displays Grades 1-5 with unique clinical descriptions of severity for each AE based on this general guidance:

Grade 1:	Mild AE
Grade 2:	Moderate AE
Grade 3:	Severe AE
Grade 4:	Life-Threatening or Disabling AE
Grade 5:	Death related to AE

Note: Severity is not equivalent to seriousness. A serious adverse event (SAE) would be any event in category 4 or 5, and any event in category 3 that required or prolonged hospitalization. Not all grades are appropriate for all AEs. Therefore, some AEs are listed with fewer than five options for Grade Selection. Grade 5 (Death) is not appropriate for some AEs and therefore is not an option.

See also http://evs.nci.nih.gov/ftp1/CTCAE/CTCAE_4.03_2010-06-14_QuickReference_8.5x11.pdf.

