8.5 SAEs/Clinical Outcomes

8.5.1 SAEs/Clinical Outcomes into the Study Database

All SAEs/Clinical Outcomes occurring until participation in study has ended are recorded on the online SAE/Clinical Outcome Reporting Form (CRF 19) through the WebDCU™. The Site PI or Study Coordinator is responsible for entering any and all SAEs into the database and updating the information (e.g., date of resolution, action taken), as needed, in a timely manner. Given the vast amount of data on AEs associated with clopidogrel, only SAEs/Clinical Outcomes will be recorded; data entry must take place within **5 days (within 24 hours for sites in the UK)** of discovery of the event.

The Hub PI for NETT sites and site PI for others are responsible for the monitoring and follow-up of all SAEs/Clinical Outcomes until resolution (or end of study for that subject) and appropriate documentation in the subject research record. In addition to performing protocol-specified follow-up,

the participating PI must review all previously reported ongoing SAEs/Clinical Outcomes to evaluate the current status.

Upon completion of the study by the subject, premature withdrawal from the study by the subject, or subject's death, all information regarding each SAEs/Clinical Outcome must be completed, if not done so earlier.

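### Protocol 8.4 defines a serious adverse event by CTCAE grade, contradicting the outcome-based definition in 8.3 and 4.6.1, so a site applying 8.4 could leave some serious events unreported

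*Protocol*

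**What the plan says.** The protocol states what makes an event serious in three places.

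- **Section 8.3** uses outcome alone. An event is serious if it is fatal or life threatening, or if it "is permanently or substantially disabling, requires or prolongs hospitalization, results in a congenital anomaly or requires intervention to prevent permanent impairment or damage". Grade is not mentioned.
- **Section 4.6.1**, under Other Serious Adverse Event, gives the same criteria for events outside the other outcome categories, again without a grade.
- **Section 8.4** assigns CTCAE grades 1 to 5 and notes that "Severity is not equivalent to seriousness". The next sentence says that an SAE "would be any event in category 4 or 5, and any event in category 3 that required or prolonged hospitalization".

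Two collection rules bear on this. Section 8.3 says "Non-serious AEs are not being collected in the POINT trial, unless they qualify as a Clinical Outcome as defined in section 4.6.1". Section 8.5.1 says that "only SAEs/Clinical Outcomes will be recorded". I found no statement of which section prevails.

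**The concern.** Most trials collect all adverse events, so one wrongly judged non-serious stays in the listing and can be reclassified later. Here, unless it is a Clinical Outcome, it has no place in the database. The wording of the seriousness rule therefore decides whether an event is recorded at all.

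The data at stake are the SAEs that are not named outcomes. They feed:

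- the coded SAE tables in the semiannual DSMB reports (SAP section 2), which use safety data as sites report them, before adjudication (SAP 13.1);
- the Clinician Event Coordinator's assessment of whether events are unexpected and related to study drug (Protocol 8.5.3);
- the tertiary analysis of SAEs together and by MedDRA class (SAP 12.5.2);
- the summaries by treatment group (SAP 13.2).

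With up to 350 sites, what counts as an SAE could vary with the section that each site follows.

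**Working it through.** No sample size, power or event figure is involved, so the check sets the two rules side by side. Grades are read by the protocol's own labels in 8.4. The term-level CTCAE text is not in the documents and is not used.

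| Event | 8.3 and 4.6.1 | 8.4 |
|---|---|---|
| Fatal (grade 5) | serious | serious |
| Life threatening or disabling (grade 4) | serious | serious |
| Grade 3, admission required or prolonged | serious | serious |
| Grade 1-2, admission required or prolonged | serious | **not serious** |
| Grade 1-3, no admission, intervention needed to prevent permanent impairment or damage | serious | **not serious** |
| Grade 1-3, no admission, congenital anomaly | serious | **not serious** |

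The last row should be close to empty, because the protocol excludes pregnant women and those at risk for pregnancy. The fourth and fifth rows carry the weight.

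**Which mismatched events are recorded anyway?** Those in a named 4.6.1 category, whatever their grade: ischemic stroke, TIA, hemorrhagic transformation, nontraumatic intracranial hemorrhage, MI, coronary revascularization, and major and minor hemorrhage as defined there. A nontraumatic bleed needing admission is major hemorrhage under 4.6.1, so the grade rule cannot remove it.

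**Which are not?** Events in the last three rows that fall outside those categories. For example, 4.6.1 limits intracranial hemorrhage to nontraumatic bleeding and excludes accidental trauma from major and minor hemorrhage. An admission for a bleed due to accidental trauma is thus captured only through the SAE rule. If it is graded 1 or 2, the two rules give opposite answers.

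**Can later steps recover it?**

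- The Clinician Event Coordinator judges seriousness (Protocol 10.3) but works from what sites submit (8.2.1, 8.5.3). That review can remove an event reported in error but cannot see one never reported.
- A site monitor who finds an unreported SAE starts the reporting (8.5.4), and 12.1.1 includes an audit against source documents as available. Each site is assured one visit, and the monitor reads the same conflicting text.

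**Effect on the comparison of arms.** Let the true risks of an SAE be p_C (clopidogrel) and p_P (placebo), and let a fraction c be recorded in both arms. The recorded difference is c(p_C − p_P), which shrinks as c falls. The recorded ratio is c·p_C / (c·p_P) = p_C / p_P, which does not change. Fewer events also mean less precision. If the mix of grades differed by arm, c would differ by arm and the ratio could move either way. The documents do not give c.

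**The case against.** The best defence is that 8.4 is a gloss within a section on severity, while the definition stands in 8.3 and is repeated in 4.6.1. Section 8.5.5 requires every event listed in 4.6.1 to be reported, and Other Serious Adverse Event is on that list with no grade. A grade 2 admission therefore has a reporting route whatever 8.4 says. An event is lost only if a site puts one sentence of 8.4 above two other sections and no monitor catches it. Form 19 and the Manual of Procedures, neither of which is in the documents, may already carry the 8.3 criteria. Treatment is double-blind and allocation is balanced within site, so differences between sites fall on both arms.

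Most of this limits the consequence and is accepted. It does not remove the contradiction. Attaching hospitalization to grade 3 alone implies that hospitalization at a lower grade is not enough, and a site could reasonably read 8.4 as the working rule.

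A reader might infer more than the documents support:

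- **That disabling grade 3 events are lost.** Section 8.4 labels grade 4 "Life-Threatening or Disabling AE", so on the protocol's own scale disabling events are already serious under 8.4.
- **That 8.4 also over-reports, for instance symptom-free grade 4 laboratory values.** That needs CTCAE text that the documents do not contain. By the protocol's label, grade 4 is serious under 8.3 too.
- **That the events are recorded nowhere and cannot be recovered.** The 4.6.1 route and source-data monitoring both exist, though neither is certain to work.
- **That a number of lost events can be stated.** The documents give no overall SAE rate, no distribution of grades and no share of sites applying 8.4.

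**Conclusion.** The contradiction is real. Section 8.4 disagrees with 8.3, with 4.6.1 and with the sentence just before it, and following it gives the wrong answer for two practical classes of event: grade 1-2 admissions, and grade 1-3 events without admission that need intervention. Congenital anomaly is a third class, mainly on paper.

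The consequence is limited to incomplete ascertainment of other SAEs at sites that apply 8.4, and no count can be derived. The components of the primary efficacy composite and of major hemorrhage are named 4.6.1 outcomes, or deaths that are serious under both rules, so the primary efficacy and primary safety analyses are not affected. Nor are the four specific events listed in SAP 13.2: death, and intracranial, major and minor hemorrhage. The documents do not show that the SAE comparison between arms is biased in a known direction on the ratio scale. With equal capture in both arms, the loss is in absolute differences and precision.

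The point should be corrected because the rule is wrong as written and easily repaired, and because this trial has no non-serious event listing to fall back on.

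**What to change.** Delete the sentence in Protocol 8.4 that defines an SAE by grade. In its place, state that seriousness is determined only by the criteria in 8.3 and 4.6.1, whatever the CTCAE grade, and that the grade is recorded in addition. Notify sites and monitors of the change.

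The cost is a one-sentence amendment, submitted for ethics review as section 11.2 requires, and a site notice. Sites that had applied 8.4 will complete a few more SAE forms. No visit, procedure or analysis changes.

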8.5 SAEs/Clinical Outcomes

8.5.1 SAEs/Clinical Outcomes into the Study Database

All SAEs/Clinical Outcomes occurring until participation in study has ended are recorded on the online SAE/Clinical Outcome Reporting Form (CRF 19) through the WebDCU™. The Site PI or Study Coordinator is responsible for entering any and all SAEs into the database and updating the information (e.g., date of resolution, action taken), as needed, in a timely manner. Given the vast amount of data on AEs associated with clopidogrel, only SAEs/Clinical Outcomes will be recorded; data entry must take place within **5 days (within 24 hours for sites in the UK)** of discovery of the event.

The Hub PI for NETT sites and site PI for others are responsible for the monitoring and follow-up of all SAEs/Clinical Outcomes until resolution (or end of study for that subject) and appropriate documentation in the subject research record. In addition to performing protocol-specified follow-up,

the participating PI must review all previously reported ongoing SAEs/Clinical Outcomes to evaluate the current status.

Upon completion of the study by the subject, premature withdrawal from the study by the subject, or subject's death, all information regarding each SAEs/Clinical Outcome must be completed, if not done so earlier.

8.5.2 Reporting Recurrent SAEs/Clinical Outcomes

If a SAE/Clinical Outcome that was previously reported on the SAE/Clinical Outcome CRF fully resolves and then recurs at a later date, the second occurrence is considered a new SAE/Clinical Outcome and a new CRF must be completed. Resolution is the normalization or return to baseline of laboratory values, clinical signs or symptoms related to the event.

8.5.3 Procedure for Expedited Reporting of SAEs/Clinical Outcomes

Clinical outcomes may be discovered during the 7-day telephone follow-up, the 30-day phone contact, the 90-day follow-up appointment, or at any point during the study period. For subjects considered lost to follow-up, efforts should be made for up to 150 days from randomization to determine if an outcome event occurred during the subject's 90 days in the study. When a clinical outcome is discovered, the Site PI is responsible for submitting it **within 5 days (within 24 hours for sites in the UK) of the discovery of the event** on the online SAE/Clinical Outcome case report form.

The Hub PI (for NINDS NETT-CCC Network sites) or Site PI (for POINT Clinical Research Collaboration (CRC) sites) are responsible for the monitoring, follow-up and appropriate documentation of all clinical outcomes until resolution or the end of study for the subject. The Site/Hub PI will work with the appropriate Site Manager to prepare an Event Packet for outcome events, including copies of discharge summaries, neurology, cardiology or other consultation notes, head imaging reports, appropriate laboratory values, and a narrative summary, plus any supplemental documentation based upon adjudication category assigned to the event, with all unique identifiers removed.

When the SAE/Clinical Outcome CRF is submitted for a fatal SAE or a clinical outcome, the appropriate Site Manager is then responsible for reviewing the information for completeness. If the information is deemed insufficient, the Site Manager will request additional information from the site.

The Site Manager will work with the Site/Hub PI to prepare an Event Packet, as described above. When the SAE/Clinical Outcome information is deemed sufficient by the Site Manager, the Clinician Event Coordinator (CEC) is charged with performing the Clinical Outcome Review (COR). The COR includes review of both Clinical Outcomes and SAEs.

The CEC, who is blinded, will then review the SAE/Clinical Outcome CRF and the Event Packet independently. If clarifications or additional information are required, the CEC will request them from the Site Manager (from either the NETT-CCC or POINT CRC), who obtains the information. The CEC can also request the information directly from the site. When all information necessary for adjudicating a clinical outcome is available and the event requires adjudication (as defined in section 8.5.5) the event will be assigned to the appropriate Adjudicators, as described in section 8.5.5.

A detailed description of the process for adjudication of clinical outcomes is found in the Manual of Procedures.

As part of the COR, the CEC will review SAEs, verifying that the accompanying narrative is complete.

The CEC, who will remain blinded throughout the trial, accesses the SAE/Clinical Outcome data. The CEC blindly reviews the data independently, but may contact the Clinical Site investigators for clarifications and additional information. The CEC designates within 72 hours of notification of the SAE/Clinical Outcome occurrence whether the SAE/Clinical Outcome is unexpected and related to the study drug.

The review process closes at the end of the 72 hours. The Clinical Site staff submits SAEs to their IRB/EC in accordance with the local guidelines and procedures.

Timelines for completion of CIOMS Form by the CRC Medical Monitor:

- 7-day reportable events- within 48 hours of receipt of the notification email (CEC assessment).
- 15-day reportable events- within 7 days of receipt of the notification email (CEC assessment).

Unexpected SAEs will be reported to the DSMB in a timely fashion and on a schedule that is determined by the DSMB.

8.5.4 Site Monitoring and SAE/Clinical Outcome Reporting

During a site monitoring visit, the NETT or CRC Site Monitor will verify appropriate documentation and reporting of SAE/Clinical Outcomes. In addition, if the site monitor identifies an unreported SAE/Clinical Outcome, appropriate documentation and reporting will be initiated as guided by the site monitor.

8.5.5 Clinical Outcome Event Reporting

All efficacy and safety clinical outcome events listed in **section 4.6.1** will be reported using the identical mechanism as described in section 8.5.3 above. In addition, Event Packets will be prepared by the site in conjunction with the NETT CCC or CRC Site Managers. These will include copies of discharge summaries, neurology consultation notes, head imaging reports, and a narrative summary prepared by the site, all with unique identifiers removed. Documents requiring translation will be checked for deletion of PHI by the country level manager, and a request for translation will be made to the CRC. The CRC will provide the translated documents back to the country level manager for upload. In addition to CRF 19 and the other core documents, additional required documents are available on the *POINT Clinical Outcome-Specific Checklists for Preparing Event Packets*, and must be included as part of the Event Packet. The Event Packet will be accessible to the Clinician Event Coordinator (CEC), who will review them for completeness.

Based on the CEC's judgment, all events will be assigned to two independent Adjudicators:

The following events will be assigned to two neurologist Adjudicators: ischemic stroke, intracerebral hemorrhage (symptomatic or asymptomatic), and other intracranial hemorrhage (symptomatic or asymptomatic).

The following events will be assigned to two cardiologist/internist Adjudicators: myocardial infarction (with or without coronary revascularization) and coronary revascularization without myocardial infarction.

The following events will be assigned to one neurologist and one cardiologist/internist Adjudicator: major hemorrhage other than intracranial hemorrhage and other serious adverse events resulting in death.

The assigned Adjudicators will review the reported event and the related Event Packet, and come to independent classifications of the event. If clarifications or additional information is/are required, the Adjudicators may contact the CEC, who will review requests and ask for additional information or clarification when necessary.

If the Adjudicators disagree with each other on the event classification, a third Adjudicator will be assigned to adjudicate the outcome event. If the third Adjudicator's classification of the event matches that of one of the two initial reviewers, this will be the final classification of the event.

If the third Adjudicator disagrees with both of the original Adjudicators, then there will be a conference call to review the discrepant event classification with the Adjudication Committee Chair. The Chair will attempt to gain consensus; however, the decision of the Chair will be the final classification of the event.

